We and others have documented that subjects with functional gastrointestinal disorders (FGID) have decreased vagal tone. A cross sectional meta-analysis of 11 articles of adult subjects with IBS (8) showed decreased vagal modulation with increased sympathetic tone. Low vagal modulatory activity occurs in other chronic pain conditions (9-13), and has been linked with poor adaptive behavior in a meta-analysis of 44 studies in 5000 children (14). In turn, poor adaptability and high pain severity in childhood more likely results in pain-related FGID, non-abdominal chronic pain, and co-morbid anxiety and depression in adulthood (15). We have also shown that the mitochondrial bioenergetics is decreased in children and adolescents with FGID and other comorbid conditions. [name] has also demonstrated in a recently accepted manuscript to *The Lancet Gastroenterology & Hepatology* that 4 weeks of auricular neuro-stimulation with an Electro Auricular Device (EAD) improves pain and functionality. We have also demonstrated that this is done through improvement in vagal tone by measuring heart rate variability (HRV) before and after EAD. In this proposal we would like to see if improving vagal modulation through a 4-week of neuro-stimulation with the EAD results in increase in mitochondrial bioenergetics and decrease in inflammatory markers.

B. SPECIFIC AIMS / HYPOTHESIS

Specific aim: determine if vagal stimulation through an electro auricular device (EAD) will improve mitochondrial bioenergetics and decrease inflammation.

Hypothesis: The vagal nerve modulates mitochondrial bioenergetics capacity through muscarinic cholinergic M2 receptors. Therefore, knowing that the mitochondrial bioenergetics is decreased in adolescents with FGID, we postulate that a 4 week neuro-stimulation with an EAD that has already shown to increase vagal tone will produce an increase in mitochondrial bioenergetics in this patient group. Furthermore, the vagus plays a critical role in the anti-inflammatory pathways, therefore increasing vagal tone should also decrease the inflammatory response.

C. BACKGROUND, SIGNIFICANCE, AND RATIONALE

Pediatric FGIDs (pFGIDs) are prevalent (16, 17) and disabling. For example IBS, just one of many pFGIDs, occurs in 6-15% of the pediatric population (18) and affects daily activity in 40% of the children (19). Chronic pain affects approximately 8.8 million children annually, with a cost of 11.8 billion, with about 1/3 of this burden

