- Subjects will meet Rome IV criteria for functional nausea, irritable bowel syndrome, dyspepsia or functional abdominal pain as determined by a pediatric gastroenterologist
- Patients must have an intact external ear that is free of infection or severe dermatological conditions, have stable vital signs for their respective age, no history of seizures and no currently implanted electrical device

Exclusion Criteria:

- Mental retardation or pervasive developmental disorder or epilepsy
- Psychosis
- Genetic or chromosomal disorders
- Pregnancy
- Subjects who admit to substance abuse during screening
- Patients with findings of peptic ulcer disease, H.pylori gastritis, celiac disease, inflammatory bowel disease, allergic disorders, or any chronic condition or medication that may cause nausea or pain
- Patients who are treated with opioids or who had any changes in their medical regimen in the past four weeks prior to study
- Patients with a history of allergy to adhesives

Study Design Overview

Subjects will undergo medical workup per standard of care. Subjects refractory to current medical therapy may be enrolled without changes to their current medical treatment. No new pharmacological agents will be added during the 4-week study period and no changes in dosing or scheduling of current therapy will be allowed during the study period. Subjects will be screened weekly for any side effects by registered nurses who are part of the Pediatric Translational Research Unit (pTRU). All subjects will be asked to notify the PI or research team with any worsening in symptoms or side effects of therapy. If symptoms worsen or fail to improve during the study or if their clinical presentation changes in any way, subjects will have the option to drop out any time, receive standard medical therapy and appropriate referrals. If per standard of care, a subject requires a change in one or several of their regular medications during the study, they will be asked to notify the research team. To monitor this, the subjects will be inquired about their medication list and doses during their weekly visits. If the medication change is determined to potentially affect the study results, the subject may be excluded from further study as determined by the PI.

Protocol and Procedures

Pre (Baseline):

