The primary investigator, a co-investigator or research coordinator will introduce the study to eligible patients seen in the CHW Autonomic and Gastroenterology Clinic during their regularly scheduled clinic visit or while

admitted to the hospital (at the end of admit). A member of the research team will explain the details and purpose of the study during an informed consent discussion. Once the patient and caregivers have had enough time to consider participation, understand all of the risks and benefits and would like to participate, they will complete the informed consent, assent and HIPAA documents.

Medical and psychological history will be obtained to verify eligibility and screen patients for alcohol, nicotine, and drug abuse following the completion of consent/assent documents. All eligible subjects will complete the questionnaires related to demographic and the Functional Disability Inventory (FDI). This will take about 5-10 minutes total to complete.

Visit 1 and 4: Subjects will undergo blood drawn for mitochondrial bioenergetics and have EAD placed. HRV will be measured before EAD placement at visit 1 and after EAD placement at visit 4. This visit will take about 60 min. They will complete the FDI again

Visit 2; 3: EAD will be changed and a new one will be placed.

Visit 5: This visit is about 2-3 month after the last EAD has been removed. At this visit they will undergo again blood drawn for mitochondrial bioenergetics, measurement of HRV and complete FDI.

The samples will be processed and stored in the laboratory of study research team members, [name] in Health Research Center, H5720.

E. TOTAL NUMBER OF HUMAN RESEARCH PARTICIPANTS PROPOSED FOR THIS STUDY AT THIS SITE AND GLOBALLY. WHAT ARE THESE NUMBERS BASED ON?

7 patients aged 12-18 years, who are being evaluated in the Gastroenterology or FGID clinic are eligible to participate in the FGID group.

F. DRUGS OR PROCEDURES

Table 1.

	Pre	Visit 1	Visit 2	Visit 3	Visit 4	Visit 5
Screening & Consent	x					
Heart Rate Variability		x			x	x
FDI	x				x	x
EAD		x	x	x	x	
Mitochondrial bioenergetics		x			x	x

All procedures will be performed in the Children's Hospital of Wisconsin (CHW) Pediatric Translational Research Unit (pTRU).

Measurements and Data Collection

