At the time of each EAD placement, a member of the research team will inquire and document current medications and doses and if subjects experienced any side effects from the EAD during the previous week. Subjects will also be asked if they wore the device for all five days and it will be documented if the device was returned to the research team.

Demographic Information

Data will be collected as part of the clinic visit and at enrollment. This includes child's date of birth, age, sex, ethnicity, and caretaker marital status. The physician assessment will also include questions about prior medical diagnoses, co-morbid symptoms and the characteristics of pain and nausea such as timing and triggers. The FDI will be performed at visit 1; 4 and 5. This instrument has demonstrated reliability and validity and have been used for both clinical and research purposes in pediatric populations.

Medical Information

Information recorded for patients is part of clinical care and includes weight, height, vital signs, medications, gastrointestinal symptoms, early life events, family history, surgeries and other medical co-morbidities.

[figure not shown]
Heart Rate Variability

HRV reflects the variability of the R-R interval in the electrocardiogram and its frequency domains (30). HRV is an indirect measure of central autonomic control and an indicator of overall psychological well-being (31). Reductions in resting HRV reflect decreases in vagal output. The high frequency range of HRV is considered representative of vagal (parasympathetic) activity and studies show altered vagal tone as measured by HRV in subjects experiencing nausea (32). All subjects will undergo a 10 minute baseline HRV measurement (five minutes supine and 5 standing) after 10 minutes of rest. Recordings will be performed supine and standing to assess baroreflex response. HRV indices such as high and low frequency domains, low/high frequency ratio and the time domain RMSSD as a surrogate of vagal tone (30) will be analyzed using Kubios software. The RMSSD values will be the primary HRV outcome and compared to baseline (pre-EAD stimulation), post-stimulation and 2-3 month later at follow up.

We will use the following HRV collection methods; *eMotion* Faros ECG Mobile 360 and the Actiwave by CamNTech. The *eMotion* Faros will primarily used, and in the event that the faros devices are not available, the Actiwave will be available as a backup device.

eMotion Faros ECG Mobile 360

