Patients will be told that they may or may not feel a slight flushing or tingling sensation after device placement. The electrode/needle arrays are implanted according to the individual's arterial and cranial nerve anatomy. The exact location of the implantation may vary slightly from person to person but is determined by both knowledge of auricular neuro-anatomy and visualization of the neurovascular bundles by transillumination (IHS, Versailles, IN, USA). The points will be targeted by four-point electrical stimulation using EAD after carefully disinfecting the ear. The small device will be positioned and secured behind the ear similar to a hearing aid, which may be covered by hair. Neurostimulation will be delivered below sensation threshold continuously for 5 consecutive days. The EAD will be applied by a trained MD or pTRU nurse. Subjects will remove the device independently at home as they are non-functioning after 5 days (5 days battery life). The subject will be asked to return the used device for proper disposal when they return for their follow-up appointment. If a device is lost or broken, the research team will attempt to schedule placement of a new EAD within 1 day if you wish. The devices are easily removed by removing the tapes and adhesives.

The EAD surgical kit consists of :

- an alcohol swab
- prep and stay swab
- round fixation plasters
- fixation plasters to fasten the generator
- Steri-strip adhesive vial
- Sterile wire harness pack
- Generator
- Tweezers
- Surgical marker
- Transilluminator

EAD placement details:

1. The EAD placement will be performed as directed and per EAD training protocol instructions identically to prior CHW IRB approved trial.
2. Before EAD placement, the subject should be advised that some discomfort is normal at first but should report if the discomfort persists or gets worse after a few minutes. The patients should be advised that they may feel a slight pulsing sensation and perhaps a warming sensation in the ear to which the electrodes are affixed. The pulsing and warming sensation may disappear after approximately 5 minutes. If the discomfort level increases the offending electrode can be slightly repositioned until the patient's discomfort level decreases to an acceptable level.
3. Device placement will take approximately 5 minutes. The patient will remain at rest for the next 5 minutes.

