and labeled with the same ID and kept together with the device package. The devices will be stored in a locked room in the division of gastroenterology. The kits will be transported by a research coordinator to the TRU on the day needed. The remaining kits will be stored in the a locked room in the GI clinic, labeled with the patient's ID. Only research coordinators within the division of gastroenterology will have access to the storage room. To track use and proper disposal of the devices, subjects will be asked to return the used device the following week (at time of the next stimulator placement or follow-up visit 5 if week 4). The doctor or research coordinator will record that device was returned and dispose it properly. The research coordinator will log this data every week on each subject as devices are returned.

Data Acquisition and Analysis

Data acquisition: we will collect EKG tracing to analyze HRV, which will include heart rate, high frequency HRV, low frequency HRV and RMSSD.

For the mitochondrial bioenergetics, we will collect basal respiration, ATP production, maximal respiration, spare respiratory capacity and extracellular respiration.

We will collect cytokines at baseline, week 4 and at visit 5

Statistical Analysis

Data Management

The data gathered will be entered into REDCap data system with each ID having a unique identifier for each participant. REDCap is a secure, web-based application for building and managing online databases. All data will be de-identified and samples will only have a unique identifier that will link the unique identifier with the patient's name.

The REDCap clinical database will be maintained by the Department of Quantitative Health Sciences, at the Children's Research Institute under the direction of [name].

EKG Data, questionnaire responses, and demographic data collection forms will be coded by a member of the research team so that all protected health information is removed. This coded data will not contain any visit dates. This coded data will be analyzed by collaborators [name]. (Ohio State University) and [name] Ph.D. (University of California, Irvine) who will not be privy to any PHI. Coded data will be shared via Onedrive. Each subject's identifying number and related electronic data will be kept on a secured, MCW password-protected database that provides access only to the PI and research staff.

Missing Data Handling

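### HRV is recorded with no device at Visit 1 but after the fourth device is placed at Visit 4, and no outcome is measured at the end of the four-week course

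*Combined protocol and SAP*

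**What the plan says.** Protocol and Procedures in section D sets out the visits. For the first and fourth: "Visit 1 and 4: Subjects will undergo blood drawn for mitochondrial bioenergetics and have EAD placed". On the timing of HRV within those visits: "HRV will be measured before EAD placement at visit 1 and after EAD placement at visit 4". Visits 2 and 3 are device changes only. Of Visit 5 it says "This visit is about 2-3 month after the last EAD has been removed".

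Table 1 in section F marks a device at Visits 1, 2, 3 and 4. It marks HRV and mitochondrial bioenergetics at Visits 1, 4 and 5 only.

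The Heart Rate Variability subsection defines the comparison: "The RMSSD values will be the primary HRV outcome and compared to baseline (pre-EAD stimulation), post-stimulation and 2-3 month later at follow up". The EAD treatment protocol gives the exposure per device: "Neurostimulation will be delivered below sensation threshold continuously for 5 consecutive days". The Study Design Overview gives the visit spacing: "the subjects will be inquired about their medication list and doses during their weekly visits". The device-tracking text in section I says when used devices come back: "at time of the next stimulator placement or follow-up visit 5 if week 4".

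The hypothesis in section B concerns the whole course: "a 4 week neuro-stimulation with an EAD that has already shown to increase vagal tone will produce an increase in mitochondrial bioenergetics".

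**The concern.** There are two linked problems.

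**Device state.** The Visit 1 recording is made with no device, the Visit 4 recording with a device that has just been placed and is active, and the Visit 5 recording again with no device. The study's premise is that this device alters vagal activity, so an on-device recording cannot be assumed to equal an off-device one. Any change involving Visit 4 combines what three earlier devices have built up with what the fourth is doing at that moment. The planned correlations of cytokine change with hfHRV and RMSSD change inherit the problem wherever they use Visit 4.

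**Exposure.** Visit 4 is the start of the fourth application, not the end of the course. The next assessment is 2 to 3 months after the last removal, so nothing is measured at the end of the four weeks that the hypothesis concerns.

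Section O counts an increase in hfHRV as part of the study's key significance. A purely acute rise at Visit 4 would appear as a gain from Visit 1 to 4 and a loss from Visit 4 to 5, exactly as a real benefit that fades would. An acute fall could hide a real gain.

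**Working it through.** The plan states no figure to reproduce here. The check is a count of exposure and of what the recordings can identify.

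**Exposure at Visit 4.** Inputs: four devices (Table 1), 5 days each (EAD treatment protocol), weekly visits (Study Design Overview). Placing Visits 1 to 4 on days 0, 7, 14 and 21 is inferred from the weekly spacing.

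- Stimulation runs on days 0–5, 7–12, 14–19 and 21–26.
- Completed at Visit 4: 3 × 5 = 15 of 4 × 5 = 20 device-days, which is 75%. The result is the same for visits 5, 7 or 8 days apart.
- The course ends at about day 26. Taking a month as 30 days, Visit 5 falls on day 26 + 60 = 86 to day 26 + 90 = 116.
- The fourth device is returned at Visit 5, so no scheduled visit falls between. Cytokines are listed at week 4 under Data Acquisition and Analysis, but the cytokine measurement text and the Statistical Analysis both place them at Visits 1, 4 and 5. That entry is therefore Visit 4, not a further visit.

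**What the HRV contrasts estimate.** Let c4 and c5 be the cumulative or persisting effects at Visits 4 and 5, and d the acute shift from having the new device in place (either sign).

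| Contrast | Estimates | Contains d? |
|---|---|---|
| Visit 1 to 4 | c4 + d | yes |
| Visit 4 to 5 | c5 − c4 − d | yes, with opposite sign |
| Visit 1 to 5 | c5 | no |

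Two of three contrasts contain d. There are four unknown means (baseline, c4, d, c5) and three recordings per subject, and c4 and d appear only as a sum. More subjects would not help. If c5 = 0, the case c4 = 0 with d = x and the case c4 = x with d = 0 give the same results: +x, then −x.

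With the Visit 4 recording made before placement, d drops out, leaving three unknowns and three recordings. With a recording both before and after placement, there are four of each.

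**Time at Visit 4.** HRV takes 10 minutes of rest plus 5 supine and 5 standing, 20 minutes in all. Placement takes 5 minutes plus 5 of rest, 10 minutes in all. Together that is 30 of the roughly 60 minutes allotted, in either order.

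**The case against.** **Acute insertion effects should be small.** Placement is followed by 5 minutes of rest, HRV is preceded by 10, and early sensations are expected to settle in about 5. Section H rates a blood-pressure drop at 1% to under 5%. If that is per subject, 7 × 0.01 = 0.07 to 7 × 0.05 = 0.35 subjects would be affected. The one syncope among 115 subjects in the earlier trial scales to 7/115 = 0.06. This stands: such events are unlikely to drive a group shift. But rest does not switch off a device that stimulates continuously for 5 days, and stimulation below sensation threshold is not stimulation without vagal effect.

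**Three devices is a reasonable point to assess.** Sections C and K report benefit after 3 weeks in the team's earlier trial. This also stands. Assessment at that point is defensible, and what remains is the label and the missing end-of-course measurement. A subject may be seen for device removal after 5 days, but no outcome is collected then.

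**An on-stimulation reading may be intended, or the wording may be loose.** Either is possible, and a pre-placement reading would fall about 2 days after the third device stops (day 19 to day 21), so it answers a somewhat different question. But no passage states an on-stimulation aim, and the middle value is called post-stimulation.

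**The reach is limited.** The specific aim is mitochondrial bioenergetics and inflammation, the mismatch is shown for HRV only, and Visit 1 to 5 is a clean off-device contrast. All of that is right and bounds the finding.

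**Conclusion.** The concern holds and should be fixed. Followed as written, the plan gives Visit 1 to 4 and Visit 4 to 5 changes in RMSSD and hfHRV that cannot be attributed to cumulative rather than acute stimulation. The Visit 1 to 5 change is unaffected. The bias equals the acute shift, whose size and sign the documents do not give. Visit 4 reflects 15 of 20 device-days, and no outcome is measured at the end of the course.

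The conclusion on device state rests on reading the Visit 4 sentence literally, with the fourth device in place during the recording. The exposure count rests on each device running its full 5 days and being finished before the next visit. The order of blood draw and FDI relative to placement is not stated, so no mismatch is claimed for those measures.

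**What to change.** Leave the device schedule as it is and make these changes to measurement and wording.

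1. In Protocol and Procedures, record the Visit 4 HRV before the device is placed, as at Visit 1. Use that value in the Visit 1, 4 and 5 comparisons and in the correlations with cytokine change.
2. If an on-stimulation reading is wanted, keep the post-placement recording as a separate, labelled measure outside those comparisons.
3. State the order of blood draw and FDI relative to placement, and keep it the same at Visits 1 and 4 for whatever is done at both.
4. In the Heart Rate Variability subsection, replace the post-stimulation label with a description of Visit 4 as following three 5-day applications, and limit conclusions from Visit 4 to that exposure. Describe Visit 5 as off-treatment follow-up after all four devices.

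Cost: one recording is reordered within an existing visit, with no added visit or blood draw, and the Visit 4 claim narrows to about three weeks of treatment. Keeping the second recording adds up to 20 minutes per subject, or 7 × 20 = 140 minutes in all. A separate end-of-course assessment would need 7 further visits. With the sample size set by budget, that is not necessary to remove the bias.

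### No medication record is scheduled at Visit 5, 2-3 months after the last device, although Visit 5 HRV, bioenergetics and cytokines are compared with earlier visits

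*Combined protocol and SAP*

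**What the plan says.** **Restriction.** Study Design Overview (section D) states "No new pharmacological agents will be added during the 4-week study period", and the same sentence continues "no changes in dosing or scheduling of current therapy will be allowed during the study period". The second clause does not repeat the 4-week limit, and follow-up is not mentioned.

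**Scheduled inquiry.** The same section says "the subjects will be inquired about their medication list and doses during their weekly visits". Measurements and Data Collection (section F) says "At the time of each EAD placement, a member of the research team will inquire and document current medications and doses". In Table 1 the device row is marked at Visits 1, 2, 3 and 4 and is blank at Visit 5.

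**Unscheduled reporting.** Where a subject "requires a change in one or several of their regular medications during the study, they will be asked to notify the research team". The handling rule is "If the medication change is determined to potentially affect the study results, the subject may be excluded from further study as determined by the PI".

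**Visit 5.** Protocol and Procedures places this visit about 2-3 months after the last device is removed: "At this visit they will undergo again blood drawn for mitochondrial bioenergetics, measurement of HRV and complete FDI". The Safety Monitoring Plan (section H) adds an inquiry about side effects, not medication, and labels the visit as post-study.

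**Use of Visit 5 data.** The Heart Rate Variability section makes RMSSD the primary HRV outcome and compares it across baseline, post-stimulation and follow-up. The analysis text under the Power heading (section I) covers vagal tone, the bioenergetic variables and cytokines at Visits 1, 4 and 5. No analysis step mentions a change in medication.

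**The concern.** The protocol itself treats a change in medication as a threat to its results. It excludes patients whose regimen changed in the four weeks before the study, restricts changes during the treatment weeks, asks about medication weekly, and lets the PI exclude a subject whose change could affect the results. The scheduled inquiry stops at Visit 4, and the ban on new drugs is tied to the 4 weeks. The longest interval in the study then begins, and it ends in a measurement that is analysed.

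The eligibility text makes later changes plausible: "Subjects refractory to current medical therapy may be enrolled without changes to their current medical treatment". A patient whose current treatment is not working may well have it altered once the 4 weeks are over. If a drug started, stopped or re-dosed between Visits 4 and 5 affects HRV, cell respiration or cytokines, a value that holds or drifts at Visit 5 could reflect that drug rather than the device. Without a record, the reader could not tell which subjects are affected. The PI also could not apply the exclusion judgement consistently if nobody is due to ask.

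**Working it through.** The plan states no figure on this point. The sample of 7 is set by budget and power is declared not applicable, so there is nothing to reproduce. The check is a comparison of the text, followed by an illustration of scale.

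**Step 1. Which measurements have a scheduled medication record?**

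| Visit | Device placed (Table 1) | Scheduled medication inquiry | HRV and blood measured |
|---|---|---|---|
| 1 | yes | yes | yes |
| 2, 3 | yes | yes | no |
| 4 | yes | yes | yes |
| 5 | no | none stated | yes |

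The Visit 1 to Visit 4 comparison is covered at both ends and between. The Visit 1 to 5 and Visit 4 to 5 comparisons are not covered after the Visit 4 placement.

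**Step 2. Could another provision fill the gap?**

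- *Subject-initiated notification (Study Design Overview).* Its end point is not defined. The Safety Monitoring Plan calls Visit 5 post-study, whereas the consent section (N) treats someone followed only for outcomes as still in the study. The stated means of monitoring this notification is the weekly visits, which end at Visit 4.
- *Medical Information (section F).* Medications are among the clinical-care items recorded, but no visit or date is attached.
- *EAD placement details, item 8.* Advice against new or as-needed anti-emetic and pain drugs has no end date. It covers those drug types only and creates no record.

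Some changes could be captured by the first two routes. None of the three is a scheduled, dated record for the interval before Visit 5.

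**Step 3. Scale.** The documents give no rate of medication change, so the rates below are assumptions. Let p be the proportion of subjects who change by Visit 5, with subjects independent and n = 7.

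- P(at least 1) = 1 - (1 - p)^7
- P(at least 2) = 1 - (1 - p)^7 - 7p(1 - p)^6

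| Assumed p | P(at least 1 of 7) | P(at least 2 of 7) |
|---|---|---|
| 0.05 | 30% | 4% |
| 0.10 | 52% | 15% |
| 0.20 | 79% | 42% |
| 0.30 | 92% | 67% |
| 0.50 | 99% | 94% |

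Each subject contributes 1/7 = 14% of the mean change. If k subjects are each shifted by s, the mean moves by (k/7)s: 0.14s for one and 0.29s for two. The size and direction of s are unknown.

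**Step 4. Would dropping changers solve it?** With n subjects and no ties or zeros, the smallest exact two-sided signed-rank p-value is 2/2^n. For n = 7 this is 2/128 = 0.016; for n = 5 it is 2/32 = 0.0625. Setting aside two subjects makes the protocol's 0.05 cut-off unreachable with that test.

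**The case against.** The strongest reply is that the gap is narrow, and several tempting readings go beyond the text.

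- A reader might infer that medication is recorded only at placements and that later changes are neither controlled nor captured. The notification request, the PI's exclusion rule and the clinical-care medication information all stand against that. The restriction on dose and schedule changes is also not explicitly limited to 4 weeks, although that is the natural reading.
- A reader might estimate how many subjects will change. For example, an assumed 10% to 30% per month over 2 to 3 months gives 7 x (1 - 0.9^2) = 1.3 up to 7 x (1 - 0.7^3) = 4.6 of 7. The arithmetic is right, but nothing in the documents supports the rate. Enrolled subjects also start with no regimen change in the previous four weeks.
- A reader might include FDI among the affected comparisons. It is collected at Visit 5, but the statistical analysis text names no FDI comparison.
- A reader might say the plan claims a sustained effect. It does not: the aim and hypothesis concern 4 weeks of stimulation, and sustained benefit is mentioned only for the team's earlier trial.

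These replies stand, as does one more: in a single-arm pilot of 7, the Visit 5 comparison is already open to time effects and regression to the mean, which a medication record would not remove. Removing changers would also condition on a post-treatment event that may depend on response.

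They do not answer the remaining point. Visit 5 is a planned comparison, the protocol regards medication change as a threat, and no one is scheduled to ask about it. With no control group, a within-subject record is the one direct means of exposing this explanation.

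**Conclusion.** The concern holds in a limited form. The plan specifies no scheduled, dated medication record for the 2-3 months before Visit 5, and no way of handling changes in that interval in the Visit 5 comparisons of RMSSD, bioenergetics and cytokines. Those comparisons may be confounded; the documents do not show that they are. The Visit 1 to Visit 4 comparison is unaffected.

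The size cannot be fixed from the documents. The chance of at least one changer among 7 runs from 30% to 99% over assumed proportions of 5% to 50%, and the effect of a change on any outcome is unknown. The conclusion rests on two readings: that the weekly visits are Visits 1 to 4, and that the undefined reporting period cannot be relied on to include follow-up. It is a cheap improvement worth making before Visit 5 data are collected, because the information may be hard to recover afterwards.

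**What to change.** 1. Add to Visit 5, in Protocol and Procedures and in Table 1, the same medication and dose question used at Visits 1 to 4, with any change since Visit 4 and its date.
2. State in Study Design Overview whether the notification rule extends to Visit 5, and reconcile this with the Safety Monitoring Plan's description of that visit as post-study.
3. In the analysis section, commit to showing Visit 5 results for all subjects as individual trajectories, with those whose medication changed marked. Any display without changers should be descriptive only, with no test attached.
4. Do not attribute Visit 5 differences to the device without that display, and say in the report that time effects and regression to the mean remain.

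The cost is a few minutes at a visit already held and one extra listing. No visit or staff is added, and no treatment rule is changed.
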